4.2. OTHER VARIABLES

These variables are for purposes of describing the study sample.

Characteristics at the screening visit of PPOIT003: age, weight/height, medical history, skin prick test (peanut, egg, milk, cashew, almond, pistachio, hazelnut, dust mite and positive and negative control), blood and faecal sample (faecal sample collected by parents at home), anaphylaxis education.

Characteristics at the F0/T3 visit: age, weight/height, medical history, skin prick test (peanut, egg, milk, cashew, almond, pistachio, hazelnut, dust mite and positive and negative control), blood and faecal sample (faecal sample collected by parents at home), anaphylaxis education.

Characteristics at the F1 time point:

- An Allergy Questionnaire collected information on allergic disease (food allergies, asthma, eczema), medications, and peanut ingestion (accidental or intentional, amount, frequency).
- Parents of children aged 0-12 years will complete a validated Food Allergy Quality of Life-Parent Form (FAQLQ-PF) to report their child's health-related quality of life from the child's perspective. Children aged 8–12 years will complete the Food Allergy Quality of Life-Child Form (FAQLQ-CF) to specifically capture quality of life from the child's perspective. Children aged 13–17 years will complete the Food Allergy Quality of Life-Teenager Form (FAQLQ-TF) to specifically capture quality of life from the teenage child's perspective.

5. STATISTICAL METHODOLOGY

5.1. F1 GENERAL METHODOLOGY

Outcomes will be analysed by treatment group, according to the group to which subjects were originally randomly allocated, regardless of subjects' compliance to treatment during the PPOIT-003 study, or crossover to other treatments. The following pairwise comparisons will be of interest:

- PPOIT vs Placebo
- PPOIT vs OIT
- OIT vs Placebo

Outcomes will also be described by the clinical outcome achieved at end of treatment in PPOIT-003 (T2 PPOIT-003), that is SU, DWSU without SU and Allergic. The following pairwise comparisons will be of interest:

(FORM: SAP template interim analysis/Version 1.1)

- SU vs DWSU
- SU vs Allergic
- DWSU vs Allergic

All demographic and continuous outcomes (collected at T0 and T3/F0) will be presented as mean and standard deviation (or medians and interquartile ranges for skewed data), whilst categorical outcomes will be presented as absolute and relative frequencies in the three treatment groups and clinical groups. Table of characteristics at T0 will be presented by treatment groups for those consented to roll over to PPOIT-003LT; Table of characteristics at T3/F0 will be presented both by treatment groups and by clinical outcome groups.

In this interim analysis, subjects who are withdrawn at the end of the PPOIT003 study will not be included in any analyses. All the outcomes will be reported in available cases who consented to roll over to PPOIT-003LT.

MEASURES OF TREATMENT EFFECT

Risk difference (RD) and relative risks (RR) between treatment groups (or clinical outcome groups) will be the measures of treatment effect for binary outcomes. Mean difference between treatment groups (or clinical outcome groups) will be the measure of treatment effect for continuous outcomes whose distribution is reasonably symmetrical. Median difference between treatment groups (or clinical outcome groups) will be the measure of treatment effect for continuous outcomes whose distribution is severely skewed.

ESTIMATION OF TREATMENT EFFECTS (BETWEEN TREATMENT GROUPS)

For binary outcomes, a generalized linear model (GLM) approach will be used and account for clustering by site, adjusted by the age group at randomisation (1-5 years; 6-10 years) and SPT wheal size (\leq 10mm; >10mm).

For continuous outcomes, the mean difference between treatment groups will be obtained by using GLM to account for clustering by site, adjusted by the age group at randomisation (1-5 years; 6-10 years) and SPT wheal size (\leq 10mm; >10mm). The median difference using quantile regression model to adjust for the stratification factors if not normally distributed.

We will also compare the QoL scores using a mixed model applied to the data at 4 timepoints (T0, T1, T3/F0, F1) and account for clustering by study site, with fixed effects for treatment, age group at randomisation and SPT wheal size, and a random effect to allow for repeated measures for each individual.

ESTIMATION OF EFFECTS (BETWEEN CLINICAL OUTCOME GROUPS)

For binary outcomes, a binary regression model will be used.

For continuous outcomes, the mean difference between the clinical outcome groups will be obtained by using linear regression. Adjusted linear regression will be used to adjust for baseline QoL score in outcome I. The median difference using quantile regression model if not normally distributed.

HANDLING OF MISSING DATA

It is anticipated that 25% of children will not continue to participate the follow-up, due to participant attrition and parent/guardian non-response. The available case analysis will be the

(FORM: SAP template interim analysis/Version 1.1)

primary one. A sensitivity analysis using Inverse Probability Weighting (IPW) and Multiple Imputation (MI) techniques will be used to handle the missing data (details in section below).

SENSITIVITY ANALYSIS

The sensitivity analysis will be performed on an intention-to-treat basis including all the children whose parent/guardian consented for follow-up, with IPW and MI techniques used to handle the missing data. It is anticipated that 25% of the original sample of 201 children will have follow-up outcomes missing. In such situations, we will use both MI combined with IPW techniques (Seaman, S.R., White, I.R., Copas, A.J. and Li, L., 2012. Combining multiple imputation and inverse-probability weighting. Biometrics, 68(1), pp.129-137.) as a sensitivity analysis. It involves two major steps:

Step 1, calculation of Inverse Probability Weights: Inverse probability weights will be calculated by treatment group using the whole sample of 201 children adopting a logistic regression model predicting participation at F1, using the following baseline variables (with no missing values): age at randomisation and SPT wheal size, clinical outcome at T2 (SU, DWSU without SU or Allergic) Once inverse probability weights are obtained, only children whose parent/guardian consented for follow-up will included in the following step, and in the final analyses.

Step 2, multiple imputation of missing data on those who participated in the F1 follow-up: The frequency and patterns of missing data will be examined. Missing values of included participants will be multiply imputed: multiple imputation models will be specified including all variables included in the analysis models (baseline stratification factors) as well as all the outcomes collected at T3/F0, and F1 follow-up. Thirty completed data sets will be imputed using multivariate normal regression including all the participants who participated in the F1 follow-up. Each dataset resulting from the multiple imputation model (a "quasi-complete dataset" because the data are complete for the included participants, but not for those excluded from MI due to not participating in the F1 follow-up) is then analysed using IPW derived at step 1. IPW reweights data so that it accounts for characteristics of excluded participants (those whose parent/guardian did not consent for the follow-up and are missing all outcome data).

By imputing for participants with few missing values, while using inverse probability weights to account for excluded participants with all missing outcome data, IPW/MI should maintain the efficiency advantage of MI while avoiding possible bias from incorrectly imputing larger blocks of data.

All outcomes listed in Table 2 will be analysed using IPW/MI as a sensitivity analysis.

SUB-GROUP ANALYSIS – AGE GROUP AT SCREENING OF PPOIT003

Available cases will be analysed by subgroups according to their age group at screening of PPOIT003 (0-5 years / 6-10 years) for all outcomes.

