4. VARIABLES

4.1. OUTCOMES

Table 1 –Outcomes description

	Outcome	Description
А	Peanut ingestion (intentional or accidental)	Binary outcome
	between T1 and F1	
		1=Yes if ingested peanut at least once over
		the 12 months period.
		0=No
В	Reaction to peanut ingestion (intentional or	Binary outcome
	accidental) between T1 and F1	1=Yes if reacted to peanut at least once
		over the 12 months period
		0=No
С	Number of reactions to peanut ingestion	Continuous outcome
	(intentional or accidental) T1 and F1 overall	
	and by severity	and Categorical outcome
		1=1 reaction
		2=2 reactions
		3=3 or more reactions
D	Use of EpiPen to treat reaction to peanut	Binary outcome
	(intentional or accidental) between T1 and F1	1=Yes if used EpiPen to treat reaction to
	(peanut at least once over the 12 months
		period
		0=No
E	Number of times using EpiPen to treat	Continuous outcome
-	reactions to peanut (intentional or accidental)	
	between T1 and F1	
F	Weekly average quantity of peanut protein	Continuous outcome
	ingested (intentional or accidental) between	
	F0 and F1	and Categorical outcome
		1=Never ingested
		2=Minimal amount (less than 1 peanut,
		<250g)
		3=Small amount (1-2 peanuts, 250-599g)
		4=Moderate amount (3-8 peanuts, 600-
		1999g)
		5=Large amount (>2000g)
G	Weekly average frequency of peanut	Continuous outcome
	ingestion (intentional or accidental) between	
	F0 and F1	and Categorical outcome
		1=Nil
		2=Less than once a month
		3=Once a month to <1/week
		4=1-2 times/week
		5=3-5 times/week
		6=>5 times a week
н	Quality of life scores – total, sub-scores	Continuous outcome. From FAQLQ-PF, tot
	(emotional impact, food anxiety, social and	score is calculated as the mean of up to 30
	dietary limitations) and FAIM total score at F1	items (some are age specific), with
		response scale from 0 (minimal impairmer
		in QoL) to 6 (maximal impairment in QoL).

		The mean scores for selected items are used to construct the sub-scores. The FAIM consists of 4 questions, scored on a 7-point scale. The FAIM total score is the mean of all items and ranges from 0 (limited severity perception) to 6 (greatest severity perception).
I	Change in quality of life scores (total, sub- scores, and FAIM) from screening in PPOIT- 003 study to F1	Continuous outcome

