5.2. F1 INTERIM ANALYSIS METHODOLOGY

Outcomes A, B, D

For these binary outcomes, they will be summarised as the number and proportion of children who had the outcome as yes between F0 and F1 by treatment groups and by clinical outcome groups.

The comparison between treatment groups will be made using a GLM approach with Gaussian error distribution (to avert convergence difficulties with low prevalence outcomes), linear link function and a cluster-robust standard error calculation to account for clustering by study site. The RD and 95% CI will be derived, adjusted by the age group at randomisation (1-5 years; 6-10 years) and SPT wheal size (≤10mm; >10mm).

The RR (with 95% CI) comparing treatments will also be estimated using a GLM approach (the "modified Poisson" approach of Zou, employing the Poisson family, a log link function and a cluster-robust standard error calculation to account for clustering by site), adjusted by the age group at randomisation (1-5 years; 6-10 years) and SPT wheal size (≤10mm; >10mm).

The comparison between clinical outcome groups will be made using a binary regression model. The RD, RR and 95% CIs will be derived.

Outcome C, F, G

For these categorical outcomes, they will be summarised as the number and proportion of children who had the outcome in each category by treatment groups and by clinical outcome groups. They will also be summarised as the median, IQR and range by treatment groups and by clinical outcome groups.

Outcomes C, E, F, G, I

For these continuous outcomes, they will be summarised as mean and SD or median and IQR by treatment groups and by clinical outcome groups as specified.

The mean difference between treatment groups will be obtained by using GLM to account for clustering by site, adjusted by the age group at randomisation (1-5 years; 6-10 years) and SPT wheal size (≤10mm; >10mm). The median difference using quantile regression model to adjust for the stratification factors if not normally distributed.

The mean difference between clinical outcome groups will be obtained by using a linear regression model. The median difference using quantile regression model if not normally distributed. For outcome I, linear/quantile regression model will be used for further adjusted for baseline QoL score.

Outcome H

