We will also compare the QoL scores between treatment groups using a mixed model applied to the data at 4 timepoints (T0, T1, T3/F0, F1) and account for clustering by study site, with fixed effects for treatment, age group at randomisation and SPT wheal size, and a random effect to allow for repeated measures for each individual.

SIGNATURES PAGE

Signature of Group Leader:

[name]

Date 04 -Jun - 2022

Print Name

[name]

Signature of Principal Investigator:

ale

Date 31-May-2022

Print Name

[name]

Signature of Trial Statistician:

Print Name

[name]

Date 10-May-2022

[name]

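### The SAP gives two different, undefined rules for choosing a mean or a median difference, so the effect measure for change in quality of life depends on the data and on the sentence followed

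*SAP*

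**What the plan says.** - **Section 5.1, Measures of treatment effect.** The mean difference is for "continuous outcomes whose distribution is reasonably symmetrical" and the median difference for "continuous outcomes whose distribution is severely skewed".
- **Section 5.1, estimation between treatment groups.** The mean difference comes from a GLM that accounts for site and adjusts for age group and SPT wheal size. Then: "The median difference using quantile regression model to adjust for the stratification factors if not normally distributed". The paragraph on clinical outcome groups has the same condition without the strata.
- **Section 5.2.** Under the heading "Outcomes C, E, F, G, I" the condition is repeated for treatment groups and again for clinical outcome groups: "The median difference using quantile regression model if not normally distributed". The only quality-of-life outcome in that list is I, the change score. Adjustment for the baseline score is stated for I only in the comparison of clinical outcome groups.
- **Section 5.2, Outcome H (scores at F1).** "We will also compare the QoL scores between treatment groups using a mixed model". This model targets means and has no median switch. Nothing is given here for clinical outcome groups.
- **Section 2.2.** The allocation codes go to the unblinded statistician after database lock at the interim analysis.

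No test or cut-off is named for skew or normality. The SAP also does not say whether raw values or residuals are judged, or whether groups are pooled.

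**The concern.** A mean difference and a median difference answer different questions, so the switch changes the effect measure and not only its standard error. The two conditions disagree for symmetrical but non-normal data and for moderate skew, both of which are plausible for a score bounded at 0 and 6. The choice is made outcome by outcome on observed data, and nothing requires it to be settled before the codes are available.

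Objective 2 is change from baseline in quality of life, which is outcome I, so a stated objective is affected. Total score, sub-scores and FAIM could end up with different measures within one table. The mixed model for the scores themselves would still report means. As written, the switch also drops the handling of site, which appears in the GLM sentence but not in the quantile-regression sentence.

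For the counts of reactions and EpiPen uses (C and E) the danger is different: the median may carry no information at all.

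**Working it through.** **1. The two rules side by side**

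| Shape of the data | Section 5.1, Measures | Sections 5.1 and 5.2, estimation |
|---|---|---|
| Normal | mean | mean |
| Symmetrical, not normal | mean | median |
| Moderately skewed | not assigned | median |
| Markedly skewed | median | median |

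The rules agree in the first and last rows only.

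**2. Group sizes.** The SAP gives 79 + 83 + 39 = 201 and expects 25% to be missing. 0.75 × 79, 83 and 39 gives about 59, 62 and 29 children; 0.75 × 201 = 150.75, taken as 151. The SAP states no SD, effect size or power for a continuous outcome, so there is no figure of its own to reproduce.

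**3. How often the switch might fire.** Two readings are assumed: Shapiro-Wilk p < 0.05 for non-normal, and absolute skewness above 1 for marked skew. Scores are simulated as means of 30 or 4 items, each a latent normal value rounded and clipped to 0-6, with 151 children and 1,000 trials per setting.

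| Outcome and assumed setting | Flagged non-normal | Absolute skewness > 1 |
|---|---|---|
| Change (I), latent mean 3 at baseline, 3 or 2 at F1 | 5-10% | 0% |
| Change (I), latent mean 2 to 1 | 7-14% | 0% |
| Change (I), strong floor at F1 (1.5 to 0.3) | 27-42% | 0% |
| F1 score (H), latent mean 3 | 7-23% | 0% |
| F1 score (H), latent mean 2 | 57-92% | 0% |
| F1 score (H), latent mean 1 | 100% | 8-10% |
| F1 score (H), latent mean 0.3 | 100% | 80-83% |

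A second family used beta-distributed 0-6 scores: baseline mean 3 and SD 1.3; F1 means from 3 down to 1; within-child correlation 0.5. It flagged change scores in 3-10% of trials.

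**4. Cost in precision if a switch is made.** Under normality the efficiency of the median relative to the mean is 2/π = 0.637. The standard error ratio is therefore √(π/2) = 1.253, an interval about 25% wider. Simulated median/mean standard error ratios (unadjusted, 59 vs 62):

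- bounded quality-of-life scores in the item-based settings: 1.21 to 1.50
- change scores, both families: 1.20 to 1.38
- other shapes: t with 5 df 1.01, exponential 0.99, Laplace 0.76, lognormal 0.59

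With the strata as covariates, median-regression intervals for beta-shaped level scores were 28-46% wider in four settings, but only 7% wider at mean 1, SD 1.

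**5. What 25% means for power.** Power = Φ(d / SE − 1.96), with an assumed d = 0.5 SD and near-normal data.

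- PPOIT vs OIT: SE = √(1/59 + 1/62) = 0.182, power 78%. With 0.182 × 1.253 = 0.228, power 59%.
- PPOIT vs placebo: SE = √(1/59 + 1/29) = 0.227, power 60%. With 0.227 × 1.253 = 0.284, power 42%.

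**6. Counts.** With an assumed share of children reacting at all (59 vs 62, 2,000 trials), the median difference was exactly 0 in 100% of trials at 10% and 20% reacting, 99.9% at 30%, and 89% at 40%.

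**The case against.** The best defence is that the Measures paragraph in section 5.1 sets the rule, and the later sentences only name the model, with non-normality as shorthand for marked skew. That reading is possible, but the text does not state it. The other condition appears four times, and the Measures paragraph itself leaves moderate skew unassigned and has no criterion.

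A reader might infer that the normality condition would send most quality-of-life outcomes to median regression. The documents do not support this. They give no distribution and name no test, and the list in section 5.2 includes only outcome I, whose change scores were seldom flagged under most assumed shapes. F1 scores were flagged far more often, but section 5.2 gives H only the mean-based mixed model for treatment groups. That exemption is not complete: the mixed model is introduced as an additional analysis, and for clinical outcome groups H has only the general rule of section 5.1, including its switch.

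A reader might also infer that median regression is always much less precise. It is not, as the heavy-tailed and strongly skewed shapes show.

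Finally, reporting medians for skewed data is common practice, and a mean describes a typical child less well when skew is strong. That stands, and is a reason to keep the median as a sensitivity analysis.

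**Conclusion.** The inconsistency is on the face of the SAP: two conditions, neither defined, leave the effect measure for outcome I to be chosen on observed data. Its practical size is conditional. Under the assumed shapes and Shapiro-Wilk at 5%, the switch would fire for change scores in roughly 3-14% of trials, or 27-42% with a strong floor at F1. If it fires for a bounded score, the standard error is roughly 20-50% larger (about 20-38% for change scores), with smaller losses or gains possible for other shapes. The true frequency cannot be known from the SAP.

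For C and E either condition is likely to select the median, and the difference is then almost always 0 if fewer than about 30% of children react. That share is an assumption; the SAP gives no reaction rate. The point should be corrected before the analysis, but it does not show that the planned results would be biased.

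**What to change.** - **Quality of life** (I, and H wherever the general rule in section 5.1 applies): make the mean difference the single prespecified effect measure and delete the normality switch. Keep the SAP's handling of site and its adjustment for age group and SPT wheal size. Report the median difference only as a sensitivity analysis.
- **Baseline score:** adjust for it in the treatment-group comparison of quality of life too, as the SAP already does for I between clinical outcome groups. This goes slightly beyond the conflict, but uses data already collected.
- **Counts C and E:** do not use the median difference as the effect measure. Use a count-appropriate measure, such as a rate ratio or a mean difference with robust errors.
- **Section 5.1:** make the Measures paragraph and the estimation paragraphs say the same thing.

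The cost is SAP wording only. The downside is that, for a strongly skewed outcome, the mean is less descriptive of a typical child; the median sensitivity analysis and the planned medians and IQRs cover this.

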This occurs after completion of the T3 visit of PPOIT-003, which coincides with the first visit of the follow-on study (F0). All subjects will be followed up for 60 months after T3/F0 (which is up to 6 years post treatment that was received in PPOIT-003). During this time, all subjects will be monitored for information on exposure to peanut/amount of peanut being eaten and allergic reactions via a mobile diary application (app) until the end of study (72 months post treatment (F5)).

A phone call will be administered at the following time points:

• Time point F1 – 12 months after F0 (24 months post-treatment)

A visit for SPT, bloods and stool will be administered at the following time points:

- Time point F2 24 months after F0 (36 months post-treatment)
- Time point F3 36 months after F0 (48 months post-treatment)
- Time point F4 48 months after F0 (60 months post-treatment)
- Time point F5 60 months after F0 (72 months post-treatment)

Note: Where a face-to-face visit is not possible (eg due to COVID-19 restrictions or other unavoidable circumstances), the visit will be conducted by phone and SPT, bloods and stool test will not be performed.

This study is expected to run for 78 months from the start of participant enrolment to the last participant finishing the study. The length of the study (i.e. follow up period) for each participant is 60 months.

The three sites will be: The Royal Children's Hospital Melbourne / Murdoch Children's Research Institute, The Women's and Children's Hospital Adelaide, Perth Children's Hospital. A maximum of 201 participants will be recruited – the study population recruited to PPOIT-003.

Study population

Subjects meeting the eligibility criteria will be recruited at end of PPOIT-003 without unblinding of PPOIT-003 treatment allocation.

Inclusion criteria

Subjects are eligible for the study if they meet all of the following criteria:

- Were randomised and received at least 1 dose of treatment in PPOIT-003
- Participated in the PPOIT-003 randomised trial
- Written informed consent from participants and/or parent/guardian.

Exclusion criteria

Subjects are not eligible for the study if they meet any of the following criteria:

- Are taking probiotic supplements (does not include formula, yoghurts and fermented foods).
- Withdrew from the PPOIT-003 study.
- Have any condition that, in the opinion of the Investigator, precludes participation for reasons of safety.

Sample size

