No formal sample size calculation is being conducted for the follow-up study. A maximum of two hundred and one (201) participants will be recruited from PPOIT-003 trial (PPOIT n=79; OIT n=83; placebo n=39).

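### The IPW/MI sensitivity analysis is labelled intention-to-treat, but children who withdrew from PPOIT-003 are barred from it and the weights as specified cannot bring them back

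*SAP*

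**What the plan says.** SAP section 2.1 lists among the exclusion criteria "Withdrew from the PPOIT-003 study". Section 5.1 (general methodology) repeats the consequence: "subjects who are withdrawn at the end of the PPOIT003 study will not be included in any analyses". Section 3 restricts the outcome analyses to randomised children who consented to roll over and have F1 data, and section 5.1 makes this available-case analysis the primary one.

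The sensitivity analysis in section 5.1 is then placed on an "intention-to-treat basis including all the children whose parent/guardian consented for follow-up", using IPW and MI for missing data. It has two steps:

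- **Step 1** fits a logistic model for participation at F1, within each treatment group, to the whole sample of 201. The predictors are age, SPT wheal size and clinical outcome at T2. All three are described as baseline variables and as complete.
- **Step 2** imputes missing values among those who took part at F1 and analyses them with the weights. Reweighting is said to work so that it "accounts for characteristics of excluded participants (those whose parent/guardian did not consent for the follow-up" and who have no outcome data).

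Section 5.1 expects 25% of the 201 to lack follow-up outcomes and gives attrition and non-response as the reasons. The table of T0 characteristics covers only children who rolled over.

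**The concern.** Intention-to-treat means that the comparison keeps every randomised child. Withdrawal from PPOIT-003 happens after randomisation and could depend on treatment. A child who withdrew cannot enter the follow-on study, so a set of consenters is already conditional on having completed the parent trial.

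The sensitivity analysis is the plan's only check on this selection, because the primary analysis uses available cases. If it carries a label that it cannot support, readers will take agreement between the two analyses as evidence that selection does no harm. The T0 table would not show them otherwise, since it omits everyone who did not roll over.

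**Working it through.** **1. The sample in Step 1.** Section 2.1 gives "PPOIT n=79; OIT n=83; placebo n=39", and 79 + 83 + 39 = 201. Step 1 therefore uses the full randomised sample. The expected loss is 0.25 × 201 = 50.25, about 50 children, which leaves about 151. With equal loss in each arm, that is about 59, 62 and 29.

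**2. The populations side by side.**

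| Place in the SAP | Children who withdrew from PPOIT-003 |
|---|---|
| 2.1, exclusion criteria | not eligible |
| 5.1, general methodology | in no analysis |
| 5.1, sensitivity analysis, opening | not in the set (consenters only), yet the set is called intention-to-treat |
| 5.1, Step 1 | in the weight model (all 201) |
| 5.1, Step 2 | not mentioned; those left out are described as non-consenters |

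The second and fourth rows cannot both be taken literally, and the plan does not say which population the weights are meant to represent.

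**3. Can the weight model be fitted to all 201?** Section 2.1 defines SU as passing T1 and T2, DWSU as passing T1 and failing T2, and Allergic as failing T1.

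- A child who left before T1 has no class.
- A child who passed T1 and left before T2 is neither SU nor DWSU.
- Only a child who failed T1 before leaving has a class.

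The T2 outcome is therefore not a baseline variable. It can be complete for all 201 only if every child reached the challenges needed for a class, or if some rule assigns one. The SAP states no such rule.

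**4. What the weights assume where they can be fitted.** A withdrawn child is represented by participants in the same arm with similar age, SPT wheal size and T2 class. The reason for leaving is not in the model, and the plan does not discuss whether the assumption is reasonable for children barred by rule.

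**5. How many children this could concern.** The SAP gives no count of withdrawn or otherwise ineligible children. For an assumed share p of the 201:

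| Assumed p | Ineligible (201 × p) | Share of the 25% if included in it (p / 0.25) | With data if the 25% comes on top (201 × (1 − p) × 0.75) |
|---|---|---|---|
| 5% | 10 | 20% | 143 |
| 10% | 20 | 40% | 136 |
| 15% | 30 | 60% | 128 |
| 20% | 40 | 80% | 121 |

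**6. Illustration of bias, on assumed inputs.** Suppose stayers have the same risk in two arms, so that they show no difference. Let d be the risk in withdrawers minus the risk in stayers. The difference among all randomised children is then (withdrawal in arm 1 − withdrawal in arm 2) × d. With assumed withdrawal of 20% against 5% and d of 20 to 40 percentage points, this is 0.15 × 0.20 = 0.03 to 0.15 × 0.40 = 0.06. If d is negative, the same sizes apply with the opposite sign. None of these inputs is in the SAP, and the sum describes an unweighted comparison.

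**The case against.** The plan is more open than the label suggests. Sections 3 and 5.1 say plainly who is analysed, and children are grouped as randomised. The weights are computed within arm, which is aimed at differential loss. The rule against including withdrawn children may have been meant for outcome analyses only; the end of Step 1 separates the weight calculation from the final analyses, which supports that reading. PPOIT-003 may also have assigned an outcome class to every randomised child.

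Part of this stands. The label affects the sensitivity analysis only, so a reader who infers that the primary comparisons are presented as intention-to-treat would be wrong. Weighting to 201 is also a real attempt at repair.

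It does not rescue the label. If the exclusion rule means outcome analyses only, the plan should say so. If a class was assigned to children without challenges, the rule should be stated, because the definitions in section 2.1 do not supply one.

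A reader might also infer that the plan puts every exclusion down to non-consent. It does not: section 5.1 excludes withdrawn children openly and also names attrition and non-response. Only the parenthesis in Step 2 mentions non-consent alone. What is missing is any count of, or allowance for, children barred by rule.

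**Conclusion.** The point holds for the sensitivity analysis. It is called intention-to-treat, and neither its membership rule nor its weights, as specified, give it that property. Sections 2.1 and 5.1 leave two different target populations standing. The correction should be made before F1 results are reported.

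The plan expects about 50 of 201 children to lack outcomes. How many of these are barred by rule is unknown; the 10 to 40 shown above is an assumed range.

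Three stronger readings are not supported:

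- **That 201 is an error.** It is stated as a maximum, and no sample-size calculation depends on it.
- **That results are biased towards active treatment by 3 to 6 percentage points.** The inputs are assumptions and either sign is possible. Children who left treatment may eat less peanut, and so react to it less.
- **That the probiotic criterion ("Are taking probiotic supplements") is a fault of this SAP.** It is an eligibility rule whose reasons and operational detail belong to the protocol, which is not at hand.

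**What to change.** 1. **Relabel.** In section 5.1, replace the intention-to-treat description with: *by randomised arm among children who completed PPOIT-003 and consented to roll over*. Limit between-arm conclusions to that population unless the weights validly target all 201.
2. **Fix the weighting target.** State whether the weights represent all 201 or only those eligible to roll over, and align the exclusion sentence in section 5.1 with Step 1. If the target is all 201, use only predictors known for every child (age, SPT wheal size, arm), or give a rule for children without a T2 class. If it is only those eligible, the T2 class can stay where it is known, but it should not be called a baseline variable. Correct the Step 2 parenthesis to cover withdrawn and ineligible children and those lost after F0.
3. **Show the selection.** Report by arm the numbers withdrawn from PPOIT-003, otherwise ineligible, not consenting and lost after F0. Present T0 characteristics for all 201 by arm and roll-over status.

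The cost is a narrower claim and one extra table, drawn from parent-trial data. Removing the T2 class from a model for all 201 also gives up a variable that may predict consent among completers, so that choice should be stated.
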